## 5.10 Follow-up evaluations (post 14+ weeks)

The patient will return to follow-up as per standard care in the NHS, with surgery completed as per standard care at week 14+. A further visit to the trial team 4-6 weeks after surgery should occur to formally record the following:

1. Pathological resection specimen findings as per the RCPATH reporting guidelines recorded on CRF
2. Neoadjuvant rectal score details
3. Any surgical and other complications – AE assessments
4. ECOG performance status
5. Investigational Blood sample taken

If patient has not received surgery due to complete clinical response, they should be followed up as per standard of care. Confirmation of their complete clinical response will be obtained from their medical records if available.

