### 13.3 Pathological Tumour response

The final resected tumour should be assessed by an experienced lower gastrointestinal pathologist and staged according to the Royal College of Pathologists recommended standard datasets as per standard of care. A pathological complete response (pCR) is staged as ypT0N0.

**Toxic death:** Any death to which IMP toxicity is thought to have a major contribution.

**Early death:** Death during the first three weeks of treatment that is not a toxic death.

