# 6. ANALYSIS

## 6.1 Outcome Definitions

Primary outcome:

- *Safety*: Binary toxicity measure defined by the occurrence of a DLT or not. This is recorded during the 13 weeks of follow-up after starting treatment. The definition of a DLT is given Appendix 4.
- *Efficacy*: MRI tumour regression grade. This is a 5 point scale that is coded as a binary variable, with scores of 1 or 2 defining a responder and scores of 3, 4 or 5 a non-responder. It is measured at 13 weeks. Patients who did not have the evaluation, or who withdrew or died prior to evaluation will be treated as non-responders. During the trial, for dose-escalation decisions a patient who has not yet reached this time point will not be included in analysis at this decision point. See Appendix 5 for the definition of MRI tumour regression grade

See Section 6.2.1 Primary analysis for definition of the optimal dose.

For dose-escalation interim analyses the safety and efficacy data is taken from the patient status update CRF. For the final determination of the MTD at the end of the trial, the safety outcome will be taken from the *BW135\_DLT\_Assessment* and *BW166\_Adverse\_Events* CRFs and the efficacy outcome taken from the *BW156\_Week13\_Pelvic\_MRI* CRF.

Secondary outcomes:

- Treatment tolerance. This is the amount of capecitabine and radiotherapy received, coded as completing at least 80% of the intended capecitabine dose and at least 20 fractions of radiotherapy. Measured at week 9. Compliance is taken from the *BW150\_Capecitabine* and *BW145\_Radiotherapy* CRF.
- MRI tumour regression grade. See definition for primary outcome, but here it will not be dichotomised. MRI tumour regression grade is taken from the *BW156\_Week13\_Pelvic\_MRI* CRF.
- Pathological complete response. This variable relates to the resected tumour so will only be observed for patients undergoing surgery. It is measured on a 4 point scale, with a score of 1 denoting pathological complete response, and scores 2:4 denoting no pathological complete response. Pathological complete response is taken from the *BW156\_Week13\_Pelvic\_MRI* CRF.
- Neoadjuvant Rectal (NAR) score. This score ranges from 0-100 with a higher score equating to a worse prognosis. It is a derived outcome which components measured on the resected tumour and at initial tumour staging. Therefore, this will only be observed for patients undergoing surgery. It is defined as

- $NAR = \frac{[5pN - 3(cT - pT) + 12]^2}{9.61}$ , where

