- cT is clinical tumour stage and is an element of the set {1, 2, 3, 4}
- pT is pathological tumour stage and takes a value in {0, 1, 2, 3, 4}
- pN is pathological nodal stage is in {0, 1, 2}
- pT and pN are taken from the *BW160\_Surgery\_Details* CRF and denoted ypT and ypN, cT is taken from the *BW070\_Screen\_Pelvic\_MRI* CRF.

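### SAP 6.1 takes pathological complete response from the pre-surgery week-13 MRI form and scores it on an undefined 4-point scale, whereas the protocol defines it as ypT0N0 on the resected specimen

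*SAP*

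**What the plan says.** **Protocol.** Section 3 lists pCR as a secondary endpoint, evaluated after resection. Section 13.3 has a lower gastrointestinal pathologist assess the specimen and defines the endpoint: "A pathological complete response (pCR) is staged as ypT0N0". Section 5.10 places surgery at week 14 or later and has the resection findings recorded at a trial visit 4-6 weeks after surgery. Of unoperated patients it says: "If patient has not received surgery due to complete clinical response, they should be followed up as per standard of care".

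**SAP 6.1, pCR.** The SAP agrees on the tissue and the patients: "This variable relates to the resected tumour so will only be observed for patients undergoing surgery". It then gives a different definition: "It is measured on a 4 point scale, with a score of 1 denoting pathological complete response", with "scores 2:4 denoting no pathological complete response". The source is stated as "Pathological complete response is taken from the *BW156\_Week13\_Pelvic\_MRI* CRF".

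**SAP 6.1, NAR score.** The next outcome in the same list uses pathological stage: "pT and pN are taken from the" surgery details form, BW160, where they are held as ypT and ypN.

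**The concern.** There are two separate faults in one definition.

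The first is the source. A form for the week-13 response scan is being asked for a result that does not exist until the tumour has been removed and examined.

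The second is the definition. ypT0N0 is a statement about the primary tumour and the nodes together. A score of 1 on an unnamed scale may or may not be the same thing, and neither document lets the reader decide. Two statisticians, one working from the protocol and one from the SAP, could report different pCR rates from the same patients.

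At stake is the reporting of a named secondary endpoint. The SAP introduction says that reported results should follow the strategy it sets out, so its text is the operative instruction even if the form name is a slip.

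**Working it through.** The documents give no pCR rate, and no sample size or power for pCR, so there is no figure to reproduce. The check compares the texts and counts stage categories.

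**1. Can the named form hold the result?**

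| Item | Timing | Where stated |
|---|---|---|
| Response MRI (BW156) | Week 13, ± 7 days | Protocol 5.9 |
| Surgery | Week 14 or later | Protocol 5.10 |
| Resection findings recorded | 4-6 weeks after surgery | Protocol 5.10 |
| pCR evaluated | After resection | Protocol section 3; SAP 2.2 |

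The upper end of the MRI window reaches into week 14, but the scan grades the tumour before it is removed, so it comes before resection in any case. A form for that scan cannot ordinarily carry the pathology result.

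**2. Could the 4-point score be the MRI grade?** No. The only MRI response scale in either document is mrTRG, which has 5 points (Protocol Appendix 2; SAP 6.1 and Appendix 5). The 4-point scale is something else, and it is not defined.

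**3. Do the two definitions agree?** The NAR coding in SAP 6.1 allows ypT in {0, 1, 2, 3, 4} and ypN in {0, 1, 2}:

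- Stage categories in all: 5 × 3 = 15.
- pCR under the protocol: ypT = 0 and ypN = 0, which is 1 category.
- pCR if score 1 grades the primary tumour only (assumption A): ypT = 0 with ypN = 0, 1 or 2, which is 3 categories.
- pCR if score 1 also requires negative nodes (assumption B): 1 category, the same as the protocol.

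Under A the protocol's category is contained in the SAP's, so the SAP rate can only equal or exceed the protocol rate. Under B the difference is zero.

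**4. How large could the difference be?** Neither document gives a rate of ypT0 node-positive disease, so the total cannot be computed. Under A, each such patient adds 1/n to the rate, where n is the number operated on. Values of n are assumed, up to the recruitment maximum of 30:

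- n = 20: 1/20 = 5.0 percentage points
- n = 25: 1/25 = 4.0 percentage points
- n = 30: 1/30 = 3.3 percentage points

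With no such patient, the effect is zero under A as well.

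**5. Are the right data available?** Yes. SAP 6.1 already draws ypT and ypN from BW160 for NAR, so ypT0N0 can be derived without collecting anything new.

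**The case against.** The strongest reply is that this is a copying slip that would correct itself. The mrTRG outcome directly above names BW156 correctly, the pCR text itself limits the variable to operated patients, and the next outcome uses BW160. Anyone extracting the data would notice that an MRI form with a 5-point grade has no 4-point pathology item. This is persuasive as to cause, and it makes it unlikely that an imaging grade would be published as pathology. It does not answer the second fault: correcting the form name still leaves an unnamed scale in place of ypT0N0.

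The 4-point item may also be a genuine collected field, since resection findings go onto the case report form, and it may be explained in the table templates (SAP Appendix 3), which are a separate document. That stands, and it is why naming the scale and reporting it separately is an acceptable alternative to deleting it.

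A reader might infer three stronger things, none of which the documents support:

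- *That pCR cannot be obtained.* This is true only of the named form. The components are on BW160.
- *That node-positive patients will be counted as complete responders.* This is possible under assumption A but not shown, because the scale is undefined.
- *That restricting pCR to operated patients is an error that hides the best responders.* A pathology endpoint needs a specimen. SAP 4.2 defines a Surgical population and SAP 6.1 states the restriction openly. Unoperated patients are still covered by week-13 mrTRG in the main population, with missing evaluations counted as non-response. Combining pCR with clinical complete response would create a new endpoint. It would rest on medical records that Protocol 5.10 expects only where available, with no stated criteria or time point. Contrasting the rates of two such endpoints would not measure an error in either.

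**Conclusion.** The SAP rule for pCR is wrong as written. Its source precedes the event it is meant to record, and its definition is neither the protocol's nor reproducible from the documents. The timing conflict and the missing definition rest on the text alone and need no assumption.

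The direction of any numerical difference depends on assumption A, under which the SAP rate is at or above the protocol rate. Under assumption B there is none. The size cannot be stated beyond the per-patient step shown above.

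The consequence is limited. SAP 6.2.2 plans no formal analysis of secondary outcomes, and pCR enters neither the toxicity model, the efficacy model, the optimal-dose definition nor the stopping rule. It should be fixed before the final analysis, but it does not threaten dose decisions or the primary result.

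**What to change.** In SAP 6.1:

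- Define pCR as ypT = 0 and ypN = 0, derived from BW160_Surgery_Details, in the Surgical population of SAP 4.2.
- Remove BW156 as the source for pCR. It remains the source for mrTRG.
- Either drop the 4-point scale, or name it, give its categories and source form, and report it separately as a regression grade.
- Beside the pCR rate, state how many patients were not operated on because of a complete clinical response, so that the denominator can be read properly. Do not build a composite endpoint from this.

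The cost is a few lines of SAP text and one derived variable from fields already collected. The count of unoperated complete clinical responders depends on the records described in Protocol 5.10, so the report should say how complete they are.

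A related point can be settled in the same revision: SAP 3.5 times the secondary analyses to completion of the end of treatment visit, usually week 13, which would come before surgery, and so before the pCR data, for the last patients.

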#### Tertiary outcomes:

- IHC staining of hexon protein coat, viral gDNA and viral mRNA gene expression in tumour cells – not covered in this SAP as analysis is not carried out by the trial statistician
- Whole genome RNA expression via RNA sequencing/ Nanostring gene expression analysis – not covered in this SAP as analysis is not carried out by the trial statistician
- ctDNA analysis exploring clearance of ctDNA and any/or emerging changes in persisting ctDNA – not covered in this SAP as analysis is not carried out by the trial statistician
- Extraction of DNA and 16S sequencing and meta-transcriptomics from faecal samples – not covered in this SAP as analysis is not carried out by the trial statistician
- Multiplex immunohistochemistry of immune cell markers – not covered in this SAP as analysis is not carried out by the trial statistician

## 6.2 Analysis Methods

### 6.2.1 Primary analysis – optimal dose and frequency of enadenotucirev that can be administered with chemoradiation

The optimal dose and frequency of enadenotucirev will be estimated using toxicity and efficacy endpoints using the main population. The same analysis is used during dose escalation as well as for final analysis.

#### **Toxicity endpoint**

Toxicity data can be used continuously throughout the trial through the use of the TiTE-CRM. We will use a 2-parameter logistic regression model to model the relationship between dose and toxicity. Data for patients who have completed the 13 week toxicity window or experienced a dose limiting toxicity will contribute full information to this model. Only partial information is known for patients who are currently on trial, within the toxicity window. This partial information contributes to the model, weighted proportionally to the observed portion of their toxicity time window and the proportion of treatment received, and treating them as not experiencing a dose limiting toxicity. The weight function is defined in the equation below as  $w_j$ .

There are 4 treatment schedules which are coded as  $i = (1, 2, 4, 6):4$ . Assuming dose 6 is the reference dose,  $d^*$ , we have treated  $J$  patients with dose  $x_j$ ,  $j=1, \dots, J$ , then we model the probability of a DLT occurring using the weighted likelihood given by

$$L(\theta) = \prod_{j=1}^J \left[ g(\theta_{x_j}) * w_j \right]^{y_j} \left[ 1 - g(\theta_{x_j}) * w_j \right]^{1-y_j}$$

where

$y_j = 1$  if a DLT occurred and 0 otherwise and

$$g(\theta_{x_j}) = \text{logit}(\theta_{x_j}) = \log(\alpha) + \beta \log(x_j/d^*)$$

$$w_j = \begin{cases} 1 & \text{if } y_j = 1 \\ \frac{1}{2} \left( \frac{u_j}{T} + \frac{v_j}{D_i} \right) & \text{if } y_j = 0 \end{cases}$$

$u_j$  = time patient has been followed for,  $T$  = total DLT window = 13 weeks

$v_j$  = amount of dose received,  $D_i$  = total dose for treatment schedule i

We assume priors for  $\alpha$  and  $\beta$  of

$$\log(\alpha) \sim \text{Normal}(\log(0.3/0.7), \text{var} = 1.44)$$

$$\log(\beta) \sim \text{Normal}(-0.1, \text{var} = 0.25)$$

$$\text{corr}(\alpha, \beta) = 0$$

We can then calculate the posterior probability of toxicity for each treatment schedule.

See Neuenschwander, Branson and Gsponer (2008) and Cheung YK and Chappell R (2000) for descriptions of the model.

### ***Efficacy endpoint***

We will use a 3-parameter logistic regression model to model the relationship between dose and efficacy. Patients are assessed for the efficacy endpoint in week 13. Patients who have not reached this time point yet will not provide any information to this model. Patients who have reached the time point for this endpoint and did not have the evaluation, or who withdrew or died prior to evaluation will be treated as non-responders.

Let  $z_j$  denote 1 if the patient responded and 0 otherwise. Then we assume

$$\begin{aligned} z_j|x_j &\sim \text{Bernoulli}(\phi_{x_j}) \\ \text{logit}(\phi_{x_j}) &\sim \gamma_1 + \gamma_2 \log(x_j/d^*) + \gamma_3 [\log(x_j/d^*)]^2 \\ \pi(\gamma_1, \gamma_2, \gamma_3) &\sim MVN \left( \begin{pmatrix} -0.5 \\ 0.5 \\ 0 \end{pmatrix}, \begin{pmatrix} 7 & 0 & 0 \\ 0 & 7 & 0 \\ 0 & 0 & 4 \end{pmatrix} \right) \end{aligned}$$

We can then calculate the posterior probability of efficacy for each treatment schedule.

### ***Definition of MTD***

At each analysis the optimal dose is defined as the minimum of the doses recommended by the toxicity and efficacy models. Define:

- A target toxicity interval as (0.2, 0.35)
- A safety criterion such that a dose is considered safe to give if the posterior probability that the DLT rate is greater than 0.35 on the dose is less than 35%, i.e.  $P(\text{risk of DLT} > 0.35 | \text{Dose, Data}) < 0.35$

Then the dose that is recommended by the toxicity model is the dose with the highest posterior probability of DLT rate lying in the target toxicity interval among those doses that satisfy the safety criterion. The treatment schedule recommended by the efficacy model is the dose with the highest posterior mean probability of response. The optimal dose is then the minimum of these 2 doses.

#### **Dose-escalation rules**

The dose suggested for the next patient is the optimal dose as defined above. However, escalation to an untried dose is subject to no dose skipping, and is only permissible if at least 2 patients have been given the dose immediately below for at least 8 weeks. There is no restriction on de-escalation.

#### **6.2.2 Secondary and tertiary analyses**

There will be no formal analysis of the secondary or tertiary objectives. See template in appendix 3 for tables and figures that will be presented.

#### **6.3 Missing Data**

Every effort will be made for complete collection and recording of data. To minimise missing data, a dedicated CRF has been designed which captures only that data required to for dose-escalation decisions.

No data imputation is planned.

#### **6.4 Sensitivity Analysis**

Sensitivity analyses will be carried out during the trial for dose-decision meetings and also for final analysis for estimating the optimal dose. In addition to repeating the analysis using the sensitivity population defined in Section 4.2, we will also repeat the analysis using different weight functions. Therefore the 2 sensitivity analyses are:

- 1) Sensitivity population and analysis using weights according to length of follow-up only, i.e. not taking into account how much dose has been received
- 2) Main population but with the most toxic scenario, i.e. we assume that all patients currently in follow-up within the DLT Window of 13 weeks have a DLT

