## **9 DOSE LIMITING TOXICITY**

### **9.1 Definition of a dose limiting toxicity (DLT)**

All patients who have received at least one dose of enadenotucirev will be evaluable for DLTs. DLTs are defined as any of the following occurring between the start of trial treatment until the Week 13 visit and by the principal investigator (PI) or agreed designee assessed as possibly, probably or definitely related to enadenotucirev or the interaction between enadenotucirev and radiotherapy and/or capecitabine. Patients who experience a DLT will receive no further trial treatment.

Dose limiting toxicities must be reported within 24 hours of the site becoming aware using the SAE form and scan and email as a PDF attachment to [[contact]](mailto:[contact]) and send an email notification to [[contact]](mailto:[contact]).

DLTs will be defined as per NCI CTCAE v4.03, except for proteinuria, and include:

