## 17 STATISTICAL CONSIDERATIONS

### 17.1 CEDAR: Evaluation of treatment schedules

The trial will use a model-based approach using the toxicity and efficacy primary endpoints to recommend the treatment schedule for future patients, and to recommend the optimal dose at the trial's conclusion.

We are using both efficacy and toxicity endpoints because although toxicity is expected to increase with increasing dose, it is possible that the relationship between efficacy and dose may not be a monotonically increasing one. This means that the optimal dose may not be the maximum tolerated dose. However, there will be no formal combination of the efficacy and toxicity data, both endpoints will contribute information independently to dose choice via dose escalation rules.

Toxicity data can be used continuously throughout the trial through the use of the TiTE-CRM. We will use a 2-parameter logistic regression model to model the relationship between dose and toxicity. Data for patients who have completed the 13 week toxicity window or experienced a dose limiting toxicity will contribute full information to this model. Only partial information is known for patients who are currently on trial within the toxicity window, or those who withdraw during treatment for reasons other than a DLT i.e. patient choice. This partial information contributes to the model, weighted proportionally to the observed portion of their toxicity time window and the proportion of treatment received, and treating them as not experiencing a dose limiting toxicity.

We will use a 3-parameter logistic regression model to model the relationship between dose and efficacy. Patients are assessed for the efficacy endpoint in week 13. Patients who have not reached this time point yet will not provide any information to this model. Patients who have reached the time point for this endpoint and did not have the evaluation, or who withdrew or died prior to evaluation will be treated as non-responders.

Specification of priors and simulation results are given in the SAP.

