### **18.4 Final analysis**

Primary analysis will be after all patients have completed their 13 week, end of treatment visit.

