### 3.5 Timing of Final Analysis

Primary and secondary outcomes will be analysed after all patients have completed their end of treatment visit, usually at week 13. Analyses for all tertiary outcomes will be documented elsewhere and will not be undertaken by the trial statistician.

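### The most-toxic-scenario sensitivity analysis has nobody to act on at the final analysis, and it leaves patients who leave follow-up early as down-weighted non-DLTs throughout

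*SAP*

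**What the plan says.** SAP 6.4 states: "Sensitivity analyses will be carried out during the trial for dose-decision meetings and also for final analysis for estimating the optimal dose". The second of its two analyses keeps the main population and the primary model and changes one thing: "we assume that all patients currently in follow-up within the DLT Window of 13 weeks have a DLT".

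Timing is set in three places. SAP 3.5: "Primary and secondary outcomes will be analysed after all patients have completed their end of treatment visit, usually at week 13". Protocol 18.4: "Primary analysis will be after all patients have completed their 13 week, end of treatment visit". Protocol 9.1 defines DLTs as events "occurring between the start of trial treatment until the Week 13 visit". SAP 6.2.1 adds: "The same analysis is used during dose escalation as well as for final analysis".

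Protocol 17.1 gives partial information to patients still inside the window "or those who withdraw during treatment for reasons other than a DLT i.e. patient choice", "treating them as not experiencing a dose limiting toxicity". SAP 6.2.1 names only patients currently on trial, although its weight formula would also apply to withdrawals. SAP 6.3 plans no imputation and SAP 6.6 no supplementary analyses.

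**The concern.** A most-toxic scenario is meant to show how far the recommended schedule depends on unobserved DLT outcomes. At an interim, most of those outcomes belong to patients still being followed. At the end, the only ones left belong to patients who withdrew consent or were lost before week 13, and the rule does not reach them.

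The final report would then show a worst case that agrees with the primary result by construction, and a reader could take that agreement as evidence of robustness. The assumption left untested is the one that treats early leavers as partial non-DLTs, and it feeds directly into the criterion that P(DLT rate > 0.35) must be below 0.35. With at most 30 patients over four schedules, a few unobserved windows can matter.

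**Working it through.** **Step 1: who is changed at the final analysis.** The rule changes patients who are (a) in follow-up and (b) inside the 13-week window. The final analysis follows all week 13 visits, and the window closes at that visit. No patient meets both conditions. Population, outcomes, weights and model are then those of the primary analysis, so the posteriors are identical. This follows from the definitions and needs no assumption about the data.

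**Step 2: who still has an incomplete window.**
- Stopped treatment only: Protocol section 6 keeps these patients in toxicity follow-up. The rule sets them to DLT at an interim while their window is open, and by the end the window has been observed.
- Withdrew consent or lost: Protocol section 6 lets all future CRFs be marked not applicable after consent withdrawal. These patients are not in follow-up, so the rule never changes them.
- Sensitivity analysis 1 uses the population in SAP 4.2, which drops non-DLT patients who missed a dose. Dropping a patient does not test a worse outcome for that patient.

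**Step 3: how much it can matter.** The plan states no figure to reproduce, because the simulation results are in a separate document. I fitted the SAP 6.2.1 toxicity model by grid integration to hypothetical data.
- Dose codes 1, 2, 4, 6 with reference 6; log(α) ~ N(log(0.3/0.7), variance 1.44); log(β) ~ N(−0.1, variance 0.25), independent.
- logit(p) = log(α) + β·log(x/6). The printed g is a logit, so I take p as its inverse.
- Likelihood contribution (w·p)^y · (1 − w·p)^(1−y); w = 1 for a DLT or a completed window, otherwise w = ½(u/13 + v/D).
- Total dose D from the Protocol 8.2 table, in 10^12 vp: 3, 6, 14 and 20 for schedules 1 to 4.
- Assumed withdrawal on schedule 4 at week 5, after 1+3+3+3+3 = 13 of 20: w = ½(5/13 + 13/20) = ½(0.385 + 0.650) = 0.517.
- The toxicity model's choice is the schedule with the highest probability of a DLT rate in (0.2, 0.35), among those with P(DLT rate > 0.35) < 0.35.

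P(DLT rate > 0.35) on schedule 4, with k withdrawals added to the completers:

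| Completers, schedules 1–4 | DLTs | k | Primary | Sensitivity 2 as written | Withdrawals set to DLT | Toxicity choice |
|---|---|---|---|---|---|---|
| 3/5/8/10 | 0/1/2/2 | 1 | 0.169 | 0.169 | 0.282 | 4, unchanged |
| 3/5/8/10 | 0/1/2/2 | 2 | 0.155 | 0.155 | 0.391 | 4 to 3 |
| 3/5/8/10 | 0/1/2/2 | 4 | 0.128 | 0.128 | 0.611 | 4 to 3 |
| 3/4/5/3 | 0/0/1/1 | 1 | 0.192 | 0.192 | 0.364 | 4 to 3 |
| 3/5/8/10 | 0/0/1/2 | 3 | 0.032 | 0.032 | 0.264 | 4, unchanged |
| 3/5/8/10 | 0/0/1/2 | 4 | 0.028 | 0.028 | 0.373 | 4 to 3 |

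Each added withdrawal lowers the primary figure (0.169, 0.155, 0.128), because it enters as a partial non-DLT.

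**Step 4: an interim, for contrast.** Completers 3/4/3/0 with no DLTs. On schedule 3, two patients are in follow-up at week 6 (w = ½(6/13 + 7/14) = 0.481) and one withdrew consent at week 5 (w = ½(5/13 + 7/14) = 0.442). P(DLT rate > 0.35) on schedule 3 is 0.013 in the primary analysis, 0.159 with sensitivity 2 as written and 0.313 if the withdrawn patient is also set to DLT. On schedule 4 the values are 0.066, 0.396 and 0.601. The rule does real work here (the toxicity choice moves from 4 to 3), but it stops short of the withdrawn patient.

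**The case against.** The strongest reply is that the uncovered group may be small and mostly unrelated to toxicity. Discontinuation for toxicity definitely attributable to enadenotucirev is already a DLT at any grade, as is missing two consecutive doses for enadenotucirev toxicity (Protocol 9.1). DLTs are assessed at early withdrawal, and SAEs are followed to resolution even after consent is withdrawn (Protocol section 6). Treatment-only withdrawals remain in follow-up. The TMG may replace withdrawals, and it may overrule the model only towards a lower schedule. Setting every remaining early leaver to DLT is therefore an extreme bound.

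Most of this stands, and it limits the likely size. It does not rescue the final-analysis use, where the result is fixed in advance whatever the withdrawals were. Replacement is optional, and SAP 3.7 keeps every dosed patient in the analysis. An extreme bound is also what the SAP says it wants from this analysis.

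A reader might infer that early withdrawals are never tested at all. The documents do not support that: treatment-only withdrawals are set to DLT at interims, and sensitivity analysis 1 removes non-DLT patients who missed doses, at interims and at the end.

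**Conclusion.** The point holds in two parts. First, at the final analysis sensitivity 2 must equal the primary analysis, so it says nothing about robustness. This is certain from the text. Second, patients whose window is never fully observed, through consent withdrawal or loss, remain down-weighted non-DLTs under sensitivity 2 at every analysis.

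The practical size is not known. It rests on an assumed number and timing of withdrawals, on hypothetical data and on the toxicity model alone; the overall recommendation is the lower of the toxicity and efficacy choices. In the examples shown, between one and four unobserved windows were needed to move the toxicity choice, and in some data sets one or three were not enough. It would be tempting to conclude that the selected schedule will be wrong or unsafe. The documents do not support that: if nobody leaves follow-up early, nothing changes. The efficacy endpoint is not affected, since withdrawals already count as non-responders.

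**What to change.** Reword sensitivity analysis 2 in SAP 6.4 along these lines: *Main population, with a DLT assumed for every patient without a DLT whose 13-week window is not fully observed, whether still in follow-up, withdrawn or lost.* Apply it at every dose-decision meeting and at the final analysis. Name withdrawals in the partial-information paragraph of SAP 6.2.1, as Protocol 17.1 does.

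The cost is a sentence or two in the SAP and one change to the analysis code, with no new data. The primary analysis is unchanged. The bound is extreme and will look less favourable whenever there are withdrawals, so the report should give the number of patients set to DLT beside the result.
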